1.0 Background

For years, plastic surgeons have struggled with two opposing goals in tissue expander breast reconstruction: protecting the implant from exposure under a thin mastectomy skin flap; and, creating an esthetically appealing breast with a full lower pole. For many surgeons, these two goals seemed mutually exclusive. Protecting the implant meant placing it completely underneath the pectoralis major and serratus muscle, forcing the implant into an unnaturally high position. On the other hand, releasing the pectoralis major muscle allows the implant to sit within the mastectomy skin flap, but exposes the lower pole of the implant to a purely subcutaneous plane.

In recent years, there has been a proliferation of bioprosthetic mesh products. Some of these products found their way into breast reconstruction^{1,2,3,4}. Plastic surgeons began using bioprosthetic mesh as a sling to allow the pectoralis major muscle to be released and then reconnected to the inframammary fold. This hammock effect protects the implant from the subcutaneous plane, takes tension off of the precarious mastectomy flap skin, and allows better control of the inframammary fold and lateral border of the breast. The additional thickness of the bioprosthetic mesh also helps to even out the thickness of the tissue overlying the implant, which is skin and muscle above and skin and mesh below^{6,7,8}.

As experience with reconstruction using bioprosthetic mesh has grown, increasing evidence suggest that mesh products may be associated with increased complication rates, particularly seroma and infection, potentially effecting not only the reconstruction, but the course of cancer treatment by delaying chemotherapy or interfering with radiation protocols^{5,9,11}. Because the mesh products consist of extracellular matrices that are created from different source materials (human, pig, cow), and are processed differently, it is logical to conclude that complication profiles, and possibly esthetic outcome, differ from product to product.

2.0 Objectives

Primary objective:

1. To determine the overall complication rate for each arm and compare the complication rate for the group of patients using different types of mesh.

Secondary objectives:

1. To determine whether esthetic outcomes differs based on the type of mesh used.

3.0 Patient Eligibility

All patients seen at the MD Anderson main campus (MDACC) and/or one of the MD Anderson regional care centers (MDACC) for immediate breast cancer reconstruction with tissue expanders will be eligible for the study.

Inclusion Criteria

Patients undergoing immediate tissue expander reconstruction following mastectomy by any of the surgeon co-investigators are eligible for the study.

Patients 18 years of age or older are eligible for the study.

Patients undergoing skin-sparing mastectomy utilizing bioprosthetic mesh are eligible for the study.

Patients who have not undergone autologous tissue breast reconstruction and intend to undergo implant only breast reconstruction.

Patients who intend to remain under the MDACC surgeon's care until completion of the reconstruction.

Exclusion Criteria

Patients with prior radiation to the breast/chest wall of the ipsilateral breast.

Patients who cannot be effectively reconstructed without the use of bioprosthetic mesh.

Patients who are current smokers.

Patients requiring additional intraoperative skin resections of greater than 1 cm beyond the skin edge as a result of mastectomy flap devascularization.

Patients who have a history of breast tissue expander or implant placement.

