7.0 Statistical Considerations

Primary endpoint

The study is designed to evaluate the overall complication rate post-tissue expander reconstruction surgery using different types of mesh. Patients who are eligible for the study will be equally randomized to the following arms: 1) Alloderm; 2) Surgimend. The primary endpoint, overall complication after tissue expander implant is defined as any of the following complications: seroma; infection; implant malposition; capsular contracture; and, hematoma.

Sample Size

Patients who are seen at MDACC for immediate breast reconstructive surgery after mastectomy will be enrolled to the study and equally randomized to the two arms when the tissue expander is implanted: 1) Alloderm; 2) Surgimend. The randomization will be stratified by surgeon in order to avoid confounding between surgeon and surgical method. A total of 398 patients will be enrolled with 199 patients for each arm. The information on overall complication observed after tissue expander implant and before

the permanent implant will be collected. The rate of overall complication for the patients using Alloderm mesh (arm 1) will be compared to the patients using Surgimend mesh (arm 2). With 199 patients in each arm the study will have 80% power to detect the difference in complication rate between 10% in the Alloderm mesh group and 20% in the Surgimend mesh group with a two-sided type I error rate of 0.05 (calculated by nQuery Advisor 7.0). The secondary objective is esthetic evaluation. The main question for the esthetic evaluation is whether the overall shape of the reconstructed breast is good. Evaluators who are blinded to the arm assignment information will grade the patients using a 5-point Likert scale (strongly disagree, disagree, somewhat agree, agree, strongly agree). Their scores will be averaged for each patient.

Analysis Plans

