9.0 Outcome

The primary endpoint, overall complication after tissue expander implant is defined as any of the following complications: seroma, cellulitis, abscess, red breast syndrome, implant malposition, capsular contracture, and hematoma. These will be defined as follows:

Seroma: Any suspected fluid collection that is either radiologically confirmed by ultrasound or clinically confirmed by drainage, or both.

Cellulitis: Any redness of the breast that resolves with antibiotics, or requires surgical removal of implant, but does not contain a purulent fluid collection.

Abscess: Any purulent fluid collection confirmed during surgical removal of implant.

Red breast syndrome: Any prolonged redness of the breast, without other symptoms of infection, which does not resolve with antibiotics, and does not go on to require removal of the implant.

Malposition: Any surgeon perceived, postoperative movement of the expander outside of the surgically created pocket.

Capsular Contracture: Any postoperative capsule formation, classified according to the Baker classification, as follows: Baker 1: normal breast; Baker 2: palpable, minimally firm capsule; Baker 3: visible, easily palpated, moderately firm capsule; Baker 4: painful, hard and breast distorted.

Hematoma: Any postoperative collection of blood requiring surgical drainage.

Secondary endpoints are related to esthetic evaluation of postoperative, standardized five (5) view clinical photos.

Esthetic Evaluation

The esthetic evaluation will be based on five standardized photographic views: frontal; right lateral; left lateral; right three-quarter: and, left three-quarter. Photographs will be taken against a blue background, standard in all clinic rooms, at a distance of five feet from the patient.

Evaluators will include three attending plastic surgeons who are not taking care of any patients in the study, three plastic surgery fellows, and three physician assistants. Their scores will be averaged for each statement. Unilaterals and bilaterals will be judged separately.

Questionnaires will evaluate the breast esthetics based on a 1 to 5 scale (strongly disagree, disagree, somewhat agree, agree, strongly agree) of the following statements:

1. The overall shape of the reconstructed breast is good.
2. The overall symmetry with the other breast is good.
3. The upper pole transition is natural in appearance.
4. The lower pole has adequate fullness and ptosis.

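### Bilateral patients enter a per-patient any-complication endpoint, but laterality is not a named baseline variable, stratum or planned adjustment, so each arm's rate mixes two risks

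*Combined protocol and SAP*

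**What the plan says.** Section 3.0 opens the trial to immediate expander reconstruction after mastectomy and does not restrict it to one side or two. Its radiation exclusion is written for one side: "Patients with prior radiation to the breast/chest wall of the ipsilateral breast". Section 9.0, on the photographs, shows that both kinds of patient are expected: "Unilaterals and bilaterals will be judged separately". That separation is confined to the esthetic scores.

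The primary endpoint (Sections 7.0 and 9.0) is met by any one of the listed complications, and everything around it is counted in patients. The size is given as "A total of 398 patients will be enrolled with 199 patients for each arm", and the comparison as "The rate of overall complication for the patients using Alloderm mesh (arm 1) will be compared to the patients using Surgimend mesh (arm 2". No sentence says how two reconstructed breasts in one patient are counted.

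Laterality is not named among the population or operative variables in Sections 5.0 and 8.0, or among the characteristics that Section 7.0 will summarize. The nearest item is a postoperative one, for procedures on the other breast. The only randomization stratum is surgeon: "The randomization will be stratified by surgeon in order to avoid confounding between surgeon and surgical method". The Cochran-Mantel-Haenszel (CMH) test adjusts for two bands of surgeon experience. The logistic model uses patient variables without a covariate list.

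**The concern.** A bilateral patient has two breasts in which a complication can occur, and a unilateral patient has one. Under a per-patient endpoint, laterality is therefore likely to be prognostic, and it is known before randomization. The plan treats the distinction as important for the secondary endpoint and leaves it out of the primary one.

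Two things are at stake. The first is precision: a usable baseline factor is left out of the analysis. The second is interpretation. The first half of the primary objective in Section 2.0 is to determine each arm's complication rate. That rate is a mixture of unilateral and bilateral risks, weighted by a bilateral share that the plan does not ask to be reported.

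**Working it through.** **The plan's own figure.** Inputs from Section 7.0: 10% v 20%, two-sided 0.05, 80% power. With pooled variance and no continuity correction, n = [1.960 × √(2 × 0.15 × 0.85) + 0.842 × √(0.10 × 0.90 + 0.20 × 0.80)]² / 0.10² = (0.990 + 0.421)² / 0.01 ≈ 199 per arm. The stated size reproduces, with power 80.0%.

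**Risk of a bilateral patient.** Let p be the risk per breast, taken as the same in every breast, and ρ the correlation between a patient's two breasts. Then P(any event) = 1 − [(1 − p)² + ρp(1 − p)], and the ratio to a unilateral patient is 1 + (1 − p)(1 − ρ). The documents do not give ρ.

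| ρ | p = 10% | ratio | p = 20% | ratio |
|---|---|---|---|---|
| 0 | 19.0% | 1.90 | 36.0% | 1.80 |
| 0.3 | 16.3% | 1.63 | 31.2% | 1.56 |
| 0.5 | 14.5% | 1.45 | 28.0% | 1.40 |
| 1 | 10.0% | 1.00 | 20.0% | 1.00 |

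**What an arm's rate contains.** The bilateral share b is not given either. Suppose 10% is a per-patient rate, b = 30% and ρ = 0. The breast-level risk is then 7.83%, a bilateral patient's risk is 1 − 0.9217² = 15.0%, and 0.7 × 7.83% + 0.3 × 15.0% = 10.0%. If instead 10% and 20% are breast-level rates, the per-patient rates at ρ = 0 run from 11.8% and 23.2% (b = 20%) to 14.5% and 28.0% (b = 50%). For example, 0.8 × 10% + 0.2 × 19% = 11.8%.

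**Chance imbalance.** The SD of the between-arm difference in bilateral share is √(2b(1 − b)/199). At b = 40% this is 4.9 points, and 1.96 SD is 9.6 points. With no mesh effect and ρ = 0, that shifts the rate difference by 9.6 × 0.09 = 0.9 points (p = 10%) or 9.6 × 0.16 = 1.5 points (p = 20%). The standard error of the difference at 10% v 20% is √(0.25/199) = 3.5 points.

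**Type I error and power.** An unadjusted chi-square test and a laterality-stratified CMH test were simulated at 199 per arm, with 200,000 runs under the null and 40,000 under the alternative. No surgeon effect was modelled, because none is given. Type I error was 0.049 to 0.051 for both tests.

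| Unit of 10%/20% | b | ρ | Unadjusted power | Stratified power | Gain (points) |
|---|---|---|---|---|---|
| patient | 30% | 0 | 81.08% | 81.40% | 0.32 |
| patient | 30% | 0.3 | 80.96% | 81.03% | 0.07 |
| patient | 50% | 0 | 80.77% | 81.04% | 0.27 |
| patient | 50% | 0.3 | 80.93% | 81.02% | 0.09 |
| breast | 30% | 0 | 87.82% | 88.19% | 0.37 |
| breast | 30% | 0.3 | 85.80% | 85.88% | 0.08 |
| breast | 50% | 0 | 91.55% | 92.08% | 0.53 |
| breast | 50% | 0.3 | 89.01% | 89.19% | 0.18 |

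Allowing for simulation error, I take the gain as about 0.1 to 0.7 points.

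**The case against.** The strongest reply is that the comparison is sound as planned. Patients are randomized 1:1, so laterality is balanced in expectation, and the ordinary standard error already covers chance imbalance. A 1.96-SD imbalance moves the difference by at most about 1.5 points at b = 40%, against a 10-point target, and only if breasts are independent. Under the same assumptions laterality explains little of the outcome variance: 0.24 × 0.09² / (0.136 × 0.864) = 1.7% at p = 10%, and 0.24 × 0.16² / (0.264 × 0.736) = 3.2% at p = 20%. All of this stands.

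The planning rates also read most naturally as per patient, since Section 7.0 speaks of the rate for patients in each arm. If they were per breast, power would be higher, not lower. This stands too, although the unit is never stated.

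A reader might infer that laterality will be unknown and that an imbalance could never be corrected. The documents do not support that. Judging unilaterals and bilaterals separately requires laterality to be known, and operative data come from the operative note or the surgery itself. The fair statement is that no baseline field is named and no adjustment is prespecified.

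On the exclusion, the ipsilateral side may simply mean any side being reconstructed. That is plausible but not written. Nor do the documents show that centers would decide differently.

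The reply does not reach the interpretation of each arm's rate. Balance between arms does not say what mixture each rate represents.

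**Conclusion.** The point holds as a low-cost improvement, not as a flaw that invalidates the trial. Bilateral patients are eligible and expected, the primary endpoint is per patient, and laterality has no planned place in its analysis. The loss is about 0.1 to 0.7 points of power, assuming 30-50% bilaterals and a correlation of 0 to 0.3, together with arm-level rates that cannot be interpreted without the bilateral share.

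Three stronger readings should be resisted. That bilateral patients carry double the risk is close to the upper limit and needs independent breasts; at p = 10% the range is 1.0 to 1.9 times. That the comparison is biased or uncontrolled is contradicted by randomization and by a type I error near 5%. That the sample size is wrong does not follow, because 199 per arm reproduces and need not change. The ratios assume equal risk in every breast and a correlation between 0 and 1.

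**What to change.** - **Sections 5.0 and 8.0:** add unilateral or bilateral reconstruction to the population variables, recorded before randomization.
- **Section 7.0, analysis plans:** add laterality as a stratum in the CMH test of overall complication, alongside the surgeon stratification, and as a covariate in the logistic model. Report complication rates by arm within unilateral and within bilateral patients.
- **Section 7.0, endpoint and sample size:** state that a patient counts once if either study breast has an event, and that the 10% and 20% rates are per patient, or else give their unit.
- **Section 3.0:** reconcile the ipsilateral wording of the radiation exclusion with the enrolment of bilateral patients. Which eligibility rule should apply is for the investigators.

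The cost is one field that the surgical plan should already hold, plus a few sentences. The small downside is more CMH strata: with two experience bands the number goes from 2 to 4, or about 398/4 ≈ 100 patients per stratum on average. The sample size is unchanged.

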5.0 Study Design

This is a prospective, randomized-to-procedure, controlled, blinded-to-esthetic evaluator trial. Information recorded and evaluated will include:

Population Variables -

- age
- body mass index (BMI)
- breast size
- past medical history
- smoking history
- tumor size and location
- mastectomy surgeon
- mastectomy method

Operative Variables -

- plastic/reconstructive surgeon
- tissue expander
- tissue expander type
- quality of skin
- additional skin resection
- intraoperative fill volume
- method of lower pole expansion
- drains

Postoperative Variables -

- duration of drains
- chemotherapy
- radiation
- number of post-op visits
- time to first expansion
- number of expansions
- final fill volume
- time to exchange
- type and volume of implant placed
- contralateral procedures performed
- nipple (yes/no)

Outcome -

- infection
- seroma
- implant malposition
- capsular contracture
- hematoma
- histologic incorporation
- esthetic evaluation (photos, blinded evaluators)

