6.0 Operative Technique

Intervention Arm:

After the mastectomy is performed, the pectoralis major muscle is elevated off the chest wall with electrocautery. After elevation superiorly and medially, the pectoralis major muscle is disinserted from the chest wall along its inferior border to the 3 or 9 o'clock position medially.

The skin envelope is evaluated. If the inframammary fold has been violated, sutures are used to secure it into its appropriate anatomic location. This is also done with the lateral breast skin.

Bioprosthetic mesh is then sewn into the inframammary fold and lateral chest wall. If Surgimend is used, then the 10 x 15 cm piece of fenestrated material is sewn to the fold, curved side along the fold, using a suture. If Alloderm (acellular dermal matrix) is used, a 6 x 12 cm piece or 6 x 16 cm piece is trimmed into a semicircle and sewn into the inframammary fold. The smooth side is placed against the implant.

The tissue expanders are then placed in the subpectoral/subbioprosthetic pocket. A drain is placed along the inferior border between the bioprosthetic mesh and the tissue expander. The superior border of the bioprosthetic mesh is closed to the inferior border of the pectoralis major muscle with a suture. An additional drain is placed in the subcutaneous pocket. Saline solution is then injected into the tissue expander to an appropriate fill volume.

Skin closure is performed.

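### Does excluding patients who need mesh undermine a trial in which both arms receive mesh?

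*Combined protocol and SAP*

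**What the plan says.** Section 3.0 lists among the exclusions "Patients who cannot be effectively reconstructed without the use of bioprosthetic mesh". The inclusion list in the same section states "Patients undergoing skin-sparing mastectomy utilizing bioprosthetic mesh are eligible for the study".

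Section 7.0 sets out the allocation: "Patients who are eligible for the study will be equally randomized to the following arms: 1) Alloderm; 2) Surgimend". Section 6.0 describes one shared technique under the heading "Intervention Arm", with mesh as a routine step ("Bioprosthetic mesh is then sewn into the inframammary fold and lateral chest wall") and separate handling instructions for each product. The primary objective in section 2.0 compares complication rates between types of mesh, and the analysis plan in section 7.0 compares two mesh arms. The scientific premise is in section 1.0: "it is logical to conclude that complication profiles, and possibly esthetic outcome, differ from product to product".

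No section describes a mesh-free arm or a switch to mesh-free reconstruction, and none gives a reason for this exclusion.

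**The concern.** An exclusion for needing mesh has an obvious protective purpose when some patients may be assigned to go without it. Here nobody is. On its face the line protects no one, and it removes the patients for whom a choice between mesh products cannot be avoided. The background asks whether products differ, and neither the objectives nor the opening sentence of section 3.0 announces a restriction to patients in whom mesh is optional.

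Two things would be at stake. The first is reach: taken literally, the result would not speak directly to patients who depend on mesh. The second is consistency of screening. The protocol gives no test for dependence on mesh, so one surgeon might apply the line strictly and another might pass over it because both arms use mesh.

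**Working it through.** **1. Are the criteria compatible?** The inclusion line concerns what is done (mesh is used). The exclusion line concerns what is necessary (no acceptable alternative exists). A patient in whom mesh is used but could have been omitted satisfies both. Section 1.0 shows that reconstruction without mesh was a real option: "Protecting the implant meant placing it completely underneath the pectoralis major and serratus muscle". The eligible set is therefore not empty, and the two lines do not contradict each other.

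**2. Can the line bias the comparison?** Section 7.0 randomizes patients who are already eligible, at the time the expander is implanted. The exclusion is thus settled before allocation and removes the same kind of patient from both arms. If surgeons read the line differently, the patient mix will differ between surgeons. Randomization is stratified by surgeon, so that variation is balanced across the arms.

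**3. Does it affect the sample size?** Inputs from section 7.0: p1 = 0.10, p2 = 0.20, two-sided alpha 0.05, n = 199 per arm. Let d = p2 − p1 and let pbar be the mean of p1 and p2.

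Power = Φ{[d√n − 1.960√(2·pbar(1 − pbar))] / √[p1(1 − p1) + p2(1 − p2)]}

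- d√n = 0.10 × 14.107 = 1.411
- 1.960 × √(2 × 0.15 × 0.85) = 1.960 × 0.505 = 0.990
- Denominator = √(0.09 + 0.16) = 0.500
- Power = Φ(0.421 / 0.500) = Φ(0.842) = 80.0%

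This reproduces the stated 80% at 199 per arm. Nothing in it depends on the exclusion line.

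**4. What would removing the line do?** The documents give neither the share of candidates who depend on mesh nor their complication rate. The figures below are assumptions used only to price removal. They do not measure any defect in the present plan. Let a share s of 10% to 30% depend on mesh, with an Alloderm-arm rate r of 10% to 20%. The blended Alloderm rate is (1 − s) × 0.10 + s × r:

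- With r = 10%, the rate stays at 10% for any s, and power stays at 80.0% for a 20% Surgimend rate.
- With s = 30% and r = 20%, the rate is 0.7 × 0.10 + 0.3 × 0.20 = 13%.

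At that 13% extreme, with 199 per arm:

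| What is held fixed | Rates | Power | n per arm for 80% |
|---|---|---|---|
| 10-point difference | 13% vs 23% | (1.411 − 1.065)/0.539 = 0.642, about 74% | 231 |
| Doubling | 13% vs 26% | (1.834 − 1.098)/0.553 = 1.331, 90.8% | 145 |

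The direction depends on which effect scale carries over to the added patients, and the documents do not settle that.

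**The case for a change.** The strongest case for acting is that the mismatch is real and cheap to address. Every randomized patient receives mesh, no rationale is written down, and a short amendment or one sentence would explain the line or delete it. The criterion is also a matter of judgement, so the enrolled population may be hard to describe afterwards. All of this stands as an observation about the text.

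It does not amount to a reason to change the plan:

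- Section 3.0 gives no rationale for any of its exclusions, so silence does not single this one out.
- A purpose is possible. The neighbouring exclusions (prior ipsilateral radiation, current smoking, larger skin resection for a devascularized flap) also narrow the population, and leaving out patients who depend on mesh could belong to the same choice of a more uniform, lower-risk group. The documents do not say so, and this is inference.
- It is equally an inference that the line survives from a design with a mesh-free comparator. The single technique heading covers both products. The description "This is a prospective, randomized-to-procedure, controlled, blinded-to-esthetic evaluator trial" is loose, but it fits arms whose mesh pieces differ in size and handling. Neither is evidence of an earlier design.
- Writing into the conclusion that it applies to patients in whom mesh is optional would restate what the eligibility criteria already imply.

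**Conclusion.** No change follows. The line sits oddly in a trial of two meshes and has no stated rationale, but the criteria are compatible, the randomized comparison is not biased, and the planned 199 per arm with 80.0% power is unaffected. Followed as written, the plan gives a sound answer for the patients it enrols. The only consequence is a narrower population, visible to anyone who reads section 3.0. Its extent cannot be derived from the documents.

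Deleting the line would trade that narrower scope for a wider population of unknown risk. On the illustrative assumptions above, power would end anywhere from about 74% to about 91%, so no clear statistical gain can be claimed. Whether to accept that trade is an eligibility decision for the sponsor.

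This conclusion assumes that eligibility is settled before the allocation is known, as the order of steps in section 7.0 implies.
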